### 1. SUMMARY

#### 1.1 Abstract and summary

The purpose of PROMIS (MRC PR11) is to trial the use of multi-parametric Magnetic Resonance Imaging (MP-MRI) as a tool in the diagnosis of prostate cancer. In particular, PROMIS aims to evaluate whether MP-MRI improves the ability to detect as well as rule-out clinically significant prostate cancer in a group of men currently advised to have prostate biopsy.

At present, men with raised serum prostate specific antigen (PSA) are advised to have a transrectal ultrasound (TRUS) guided biopsy. This study will investigate whether imaging prior to biopsy can be incorporated into the existing diagnostic pathway for prostate cancer. We will evaluate whether men with a raised PSA, or other risk factors for harbouring prostate cancer, should first undergo a MP-MRI in order to select a group that could safely forego prostate biopsy. In addition, this study will evaluate the ability of MP-MRI to identify lesions for selective biopsy.

In order to evaluate the diagnostic accuracy of MP-MRI (index test) against the TRUS guided biopsy (current standard test) both procedures need to be compared to a reference standard. This reference standard needs to be accurate at both detecting and ruling-out prostate cancer and amenable to application to all men at risk. Template Prostate Mapping (TPM) meets the necessary performance characteristics of such a reference test. It is performed under a general/spinal anaesthetic.

By design, PROMIS, conforms to a validating paired cohort study (see Oxford Centre for Evidence-based Medicine, 'Levels of Evidence', 1b, http://www.cebm.net/index.aspx?o=1025). All men in the study will have a MP-MRI (index test), followed by both a TPM biopsy (reference test) and a standard TRUS guided biopsy (current standard test). These 3 tests will be assessed and reported independently from each other.

[figure not shown]
The study is divided into a pilot and a main phase. The pilot will be run in two centres, University College London Hospitals NHS Foundation Trust and North Hampshire Hospitals NHS Trust and aims to recruit 50 patients over one year. The pilot will assess recruitment and the safety of administering the tests, particularly the combined prostate biopsy (CPB) procedure of TPM and TRUS under general/spinal anaesthesia. Continuation to the main phase will depend on an independent review of the data.

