#### 2.2 Diagnostic pathway

At present, a man is judged to be at risk of harbouring prostate cancer if he has any of the following: a raised serum PSA level (the majority), an abnormal digital rectal examination (DRE), a positive family history or a specific ethnic risk profile. Such men are currently advised to have a transrectal ultrasound (TRUS) guided prostate biopsy. Between 59,000 and 80,000 men have a TRUS biopsy in the UK each year. Men undergo prostate biopsy in the absence of accurate imaging that can visualise a suspicious lesion. Ultrasound is used to identify the prostate, not the suspect lesion. The result is that biopsies are taken 'blindly' from areas of the gland. This approach (Figure 1, current diagnostic pathway) contrasts markedly with that used for other cancers. The typical approach is either to see (e.g. at endoscopy) or to image (e.g. using mammography) a suspect lesion, and then to biopsy it directly.

[figure not shown]
In PROMIS, we will determine whether it is appropriate that men with a risk factor for harbouring clinically significant cancer should first undergo MP-MRI to select who should, or should not, have a prostate biopsy. MP-MRI would therefore act as a triage test (Figure 1, proposed diagnostic pathway). This could offer several important advantages:

- Less over-diagnosis, i.e. fewer *clinically insignificant* prostate cancers detected by avoiding unnecessary biopsy of men who do not have clinically significant cancer.
- Less over-treatment as fewer *clinically insignificant* prostate cancers are detected.
- Increased detection of *clinically significant* prostate cancers by directing biopsies to areas of the prostate that appear abnormal on MP-MRI.
- Improved characterisation of individual cancers due to more representative biopsy sampling.

• Reduced complications (sepsis and bleeding) as fewer men biopsied and fewer biopsies taken in men that are biopsied.

The overall result also has the potential to offer a more cost-effective use of NHS resources. This area of research has been designated as important both by the UK's National Institute for Health and Clinical Excellence (Prostate Cancer Management Guidelines, 2009) and the US National Institute of Health - National Cancer Institute.

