#### 6.1 Visit 2: MP-MRI

The MP-MRI will be carried out in a 1.5 or 3.0 Tesla scanner with the patient in the supine position. T2, DW and DCE scans will be acquired.

The primary analysis will be based on the local site radiology report. Clinical details including PSA and DRE findings will be known to the reporter. In addition, to determine inter-observer variability and as a quality control measure, double-reporting will be carried out centrally by a number of designated radiologists who will also know clinical details of the case.

Scans will be reported to the MRC CTU on the MRI case report form (CRF) and kept locally by the local site radiologist. Radiologist should refer to the MRI Standard Operating Procedure (SOP). Scans deemed unreadable should be repeated in the same patient whenever possible and appropriate to do so. Cases where MRI scans could not be done/are not readable and are not repeatable should be noted on the MRI CRF that is sent to the MRC CTU (Please see Withdrawal section 6.10 for further information).

An overall whole prostate score will be given (1-5) to indicate the probability of clinically significant cancer:

- Highly likely benign (1).
- Likely benign (2).
- Equivocal (3).
- Likely malignant (4).
- Highly likely malignant (5).

For the primary outcome, an overall score of 3 or more will be used to indicate the possible presence of clinically significant cancer. This reflects the level at which further tests (e.g. biopsy) would be considered if MP-MRI were to be introduced into the diagnostic pathway in the future.

Each reporter will have access to a workstation with mean curve software to be used in the scoring of suspicious lesions (up to a maximum of 6). Images will be reported in sequence: T2  $\rightarrow$  T2+DW  $\rightarrow$  T2+DW+DCE and a separate report produced for each combination of sequences.

For sector analysis, the prostate will be divided into 12 regions of interest (ROI):

- Apex: Right/Left & Anterior/Posterior.
- Mid: Right/Left & Anterior/Posterior.
- Base: Right/Left & Anterior/Posterior.

Radiologists will use the 1-5 score for each ROI.

For each lesion found, the following will be recorded:

- Longest axial diameter.
- Lesion volume.
- Apparent Diffusion Coefficient (ADC).
- DCE-MRI curve shape.

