#### 9.1 Outcome Measures

#### 9.1.1 Primary

There are two primary outcomes in this trial as both are of fundamental importance to decisions regarding the future use of MP-MRI in the diagnostic pathway for the prostate cancer:

- Proportion of men who could safely avoid biopsy as determined by specificity and negative predictive values (NPV)
- 2. Proportion of men correctly identified by MP-MRI to have clinically significant prostate cancer as determined by sensitivity and positive predictive values (PPV)

For the primary outcomes we take DEFINITION ONE (A dominant Gleason pattern  $\geq$  4 and/or a cancer core length  $\geq$  6 mm, see section 2.6) as the criteria for clinically significant prostate cancer as assessed by TPM, the most appropriate reference standard.

Alongside these outcomes, the accuracy of TRUS will also be reported in terms of sensitivity, specificity, NPV, and PPV as listed in the section below. In addition, a head-to-head comparison of the sensitivity of MP-MRI versus TRUS guided biopsy (current standard) will be performed amongst men diagnosed with clinically significant prostate cancer according to TPM.

For the primary outcome, a score of 3 or more on MRI will be used to define a potentially clinically significant cancer (see section 6.1 for details). A dominant Gleason pattern  $\geq$  4 and/or a cancer core length  $\geq$  6 mm will be used for clinically significant cancer (see DEFINITION ONE section 2.6) for the biopsies.

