#### 9.3.2 Primary analysis of the main study

The primary analysis will be based on all evaluable data, excluding men without all three test results and any data rejected as part of the external MP-MRI QC/QA process (see section 6.6.1).

The sensitivities, specificities and predictive values will be calculated for MP-MRI based on the overall cancer score for MP-MRI and DEFINITION ONE for clinically significant cancer on TPM biopsy. Results will be presented in a 2 by 2 table (as shown below in Table 4) and estimates will be presented together with 95% confidence intervals (CI).

Table 4: 2 by 2 tables to	demonstrate accuracy of MP-MRI	with respect to TPM

		MP-MRI		
		+ve	-ve	Total
TPM	+ve	а	b	a+b
	- ve	С	d	c+d
	Total	a+c	b+d	

**Specificity** = d / (c+d) where, d = number of men testing negative on MP-MRI and negative for clinically significant cancer on TPM, c = number of men testing positive on MP-MRI who do not have clinically significant cancer on TPM.

**Negative Predictive Value (NPV)** = d / (b+d) where, d = number of men testing negative on MP-MRI and negative for clinically significant cancer on TPM, b= number of men testing negative on MP-MRI who have clinically significant cancer on TPM.

**Sensitivity** = a / (a+b) where, a = number of men testing positive on MP-MRI and positive for clinically significant on TPM, b = number of men testing negative for MP-MRI who have clinically significant cancer on TPM.

**Positive Predictive Value (PPV)** = a / (a+c) where, a = number of men testing positive on MP-MRI and positive for clinically significant on TPM, c = number of men testing positive on MP-MRI who do not have clinically significant cancer on TPM.

**Comparison of TRUS guided biopsy and MP-MRI**: McNemar's test will be used to compare the agreement between MP-MRI and TRUS biopsies in the subset of men found to have clinically significant prostate cancer according to DEFINITION ONE. Results will be presented in a 2 by 2 table as shown below in Table 5.

		MP-MRI		
		+ve	-ve	Total
TRUS	+ve	r	S	r+s
	- ve	t	u	t+u
	Total	r+t	s+u	Npairs

Table 5: 2 by 2 table demonstrating the comparison of TRUS guided biopsy and MP-MRI

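### The MP-MRI versus TRUS comparison sets no location condition, so as support for better directed detection its margin is an upper bound; a location-matched man-level analysis should be added

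*Protocol*

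**What the plan says.** Section 6.1 gives each man one whole-prostate score, and "an overall score of 3 or more will be used to indicate the possible presence of clinically significant cancer". Section 9.3.2 calculates accuracy "based on the overall cancer score for MP-MRI and DEFINITION ONE for clinically significant cancer on TPM biopsy" and defines cell a of Table 4 as "a = number of men testing positive on MP-MRI and positive for clinically significant on TPM". Table 5 cross-classifies MP-MRI and TRUS among men with DEFINITION ONE cancer on TPM and applies McNemar's test. Neither table carries a location condition. For TRUS the criterion is histological: section 9.1.1 states that dominant Gleason pattern and core length "will be used for clinically significant cancer (see DEFINITION ONE section 2.6) for the biopsies". Primary outcome 2 in the same section is the "Proportion of men correctly identified by MP-MRI to have clinically significant prostate cancer as determined by sensitivity" and PPV.

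The protocol gives MP-MRI two roles. Section 2.2 calls it a triage test. The same section also expects more detection of significant "prostate cancers by directing biopsies to areas of the prostate that appear abnormal on MP-MRI", and section 1.1 says "this study will evaluate the ability of MP-MRI to identify lesions for selective biopsy". A main objective in section 1.1 is a better detection rate for the MP-MRI based pathway than for TRUS, and section 9 makes better detection one of two conditions for recommending MP-MRI.

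Location is not ignored. Radiologists score 12 regions of interest (ROI), and section 9.3.3 item 2 gives accuracy for each ROI under three matching rules: nearest neighbourhood, complete match and left/right.

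**The concern.** Take a man with an MP-MRI score of 3 at the left base anterior only, whose sole DEFINITION ONE cancer on TPM is at the right apex posterior. He is a true positive in Table 4. If TRUS misses his cancer, he enters the TRUS-negative, MP-MRI-positive cell of Table 5 and counts in favour of MP-MRI. For triage that is correct, because he has significant cancer and the scan sends him to biopsy. For the claim that directed biopsy finds more cancer, the scan did not point to the cancer it is credited with.

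The credit is one-sided. A TRUS positive is cancer seen in a core, so it cannot be coincidental in this sense. Section 9.3.3 item 2 does not close the gap: as written it reports by ROI, states no man-level location-matched sensitivity, and does not feed the comparison with TRUS. Table 5 would therefore be the only man-level evidence offered for directed detection.

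**Working it through.** **Inputs from the protocol.** TRUS sensitivity 48%, MP-MRI sensitivity 70%, 107 cases, 90% power, two-sided 5% (section 9.2.3). Discordant cells under independence 0.364 and 0.144 (Appendix V, Table A1). Prevalence 15% (section 9.2.1). Specificity 77% and the alternative MP-MRI sensitivity of 75% (section 9.2.2).

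**Reproducing the plan.** Let s be the sum of the discordant cells and d their difference: s = 0.364 + 0.144 = 0.508 and d = 0.22.

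n = [1.960√s + 1.282√(s − d²)]² / d² = [1.960√0.508 + 1.282√0.4596]² / 0.0484 = 106.1, rounded up to 107 cases.

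107 / 0.15 = 713.3, rounded up to 714 men. Power at 107 cases is 90.3%. The other four rows of Table A1 (48, 66, 153 and 170 cases) also reproduce, so there is no arithmetic error.

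**Direction.** If a matched ROI scored 3 or more always comes with an overall score of 3 or more, requiring a match can only remove MP-MRI positives. TRUS stays at 48%. The 22-point margin is then an upper bound, whatever the off-target rate.

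**Size, under an assumption.** The documents give no off-target rate. Let f be the probability that a man whose significant cancer is not seen still receives an unrelated positive score, independently. Then S = L + (1 − L)f, so L = (S − f)/(1 − f), where S is any-location and L location-matched sensitivity. Power at 107 cases is Φ{[d√107 − 1.960√s] / √(s − d²)}, with discordant cells 0.52L and 0.48(1 − L) under independence from TRUS.

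For S = 70%:

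| f | L | Margin over TRUS (points) | Power, independence |
|---|---|---|---|
| 5% | 0.65/0.95 = 68.4% | 20.4 | 85% |
| 10% | 0.60/0.90 = 66.7% | 18.7 | 78% |
| 15% | 0.55/0.85 = 64.7% | 16.7 | 69% |
| 23% | 0.47/0.77 = 61.0% | 13.0 | 47% |

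The last row sets f to 1 − 0.77, the false-positive rate implied by the planned specificity.

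**How far this depends on the other assumptions.**
- Agreement with TRUS: if only 1% of cases are TRUS-only (the first row of Table A1), power at f = 23% is about 95%.
- MP-MRI sensitivity: with S = 75% and independence, power is 97%, 95%, 92% and 82% for the four values of f.
- Chance matches: the table gives no credit for off-target marks that match by luck. At f = 23% and S = 70%, crediting 1 in 12 (exact ROI) gives 61.0 + 9.0/12 = 61.8% and power 52%. Crediting 1 in 2 (same side) gives 61.0 + 9.0/2 = 65.5% and power 73%. The same steps from S = 75% give 68.1% and 71.3%, with power 84% and 93%.

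**The case against.** The strongest reply is that man-level counting is the intended quantity. Section 2.2 describes triage, section 6.1 ties the threshold of 3 to the point where further tests would be considered, and primary outcome 2 counts men, not lesions. Section 2.4.3 criticises earlier work for treating regions as independent, which favours a man-level primary. All of this stands, and it is why the primary sensitivity should not change.

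A reader might go further and infer that the primary sensitivity is inflated, or that the study is underpowered. The documents do not support either. For triage an off-target mark is no bias, the planned comparison keeps its 90% power, and the lower power figures apply only to a location-matched version. Nor can one say that the man in the example would have his cancer missed: directed biopsy is listed as a possible advantage, and no text says that men with positive scans would have targeted cores only.

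The objection to the size also largely stands. The 23% rate comes from men without DEFINITION ONE cancer, some of whom may have real smaller lesions, so it need not apply to unrelated marks in men with cancer. Section 9.2.4 regards positive agreement between the tests as more realistic than independence, and section 9.2.3 calls 70% conservative. Whether the planning sensitivities were whole-gland or location-matched in their sources cannot be seen from the protocol.

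Finally, matching rules are already planned, and section 9.3 leaves full detail to an analysis plan not shown here. That weakens any charge of omission. But the protocol itself fixes Table 5 and the detection claim, and the planned matching is stated per ROI only.

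**Conclusion.** The point holds in a limited form. Sections 9.1.1 and 9.3.2 are sound for triage. The same Table 5 is asked to support better detection through directed biopsy, and there it gives an upper bound, because it sets a location-free imaging score against histology. The direction rests only on the overall score being at least as high as any matched ROI score. The size is unknown: under the independence model with S = 70% the loss runs from under 2 points at f = 5% to 9 points at f = 23%, and power stays above 80% at every f shown if S is 75% or if TRUS-only cases are rare. This is a worthwhile improvement to the analysis, not a flaw in the sample size or in the primary outcome.

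**What to change.** Leave the primary man-level analysis as it is. Add to section 9.3.2 or 9.3.3 a pre-specified supporting analysis. In it, a man is MP-MRI positive only if his overall score is 3 or more and at least one ROI scored 3 or more matches a TPM core meeting DEFINITION ONE. Use the protocol's own rules: nearest neighbourhood as the main rule, with complete match and left/right as sensitivity analyses. Report the resulting sensitivity beside the any-location figure, and repeat Table 5 and McNemar's test with it. State that the any-location result supports triage and that claims about directed detection or selective biopsy rest on the location-matched result.

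The cost is some wording and one extra analysis. ROI scores and individually identified TPM cores are already collected (sections 6.1 and 6.2), so no men or procedures are added. The downside is a possibly smaller margin for MP-MRI, which is better fixed by rule before the results are known.

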#### 9.3.3 Secondary analysis of the main study

1. All analyses performed for DEFINITION ONE (primary analysis) will be repeated for DEFINITION TWO.

2. The sensitivity, specificity and predictive values of MP-MRI will be presented (according to DEFINITIONS ONE and TWO) for each of the 12 ROI (see section 6.1). Agreement between the MP-MRI and TPM in identifying clinically significant cancer in the same region will be based on a nearest neighbourhood approach. Sensitivity to this approach will be tested by also presenting results according to complete match (most stringent rule) and using a left/right rule (less stringent rule).

3. The sensitivity, specificity and predictive values of MP-MRI will be presented (according to DEFINITIONS ONE and TWO) for each of the individual MRI reporting sequence combinations, namely T2, T2+DW and T2+DW+DCE.

4. Inter-observer reliability: Coefficients of reliability will be derived to determine intra-observer and interobserver reliability. Although the local radiologist will report all images from their centre, the pilot data (and a sample from the main study as required) will be used to evaluate reliability, so as to reduce the burden on reporters that would result if all reporters had to assess each scan twice. All MRI assessments in the pilot will be randomly re-allocated to five central radiologists in equal numbers for re-assessment. The radiologists will perform the re-assessments blind to the results of the first assessment and first examiner. A proportion of MRI scans will therefore be re-examined by the same examiner. In the main phase, at least a proportion of MRI assessments will be randomly re-allocated to one of five other radiologists for re-assessment to be reported blind to any previous assessments or histology. None will be blinded to clinical details (i.e. PSA and DRE findings).

## **10. COST-EFFECTIVENESS**

#### **10.1 Introduction**

Two important health economic consequences arise from the current diagnostic pathway. First, many men receive a diagnosis of a clinically insignificant prostate cancer and, as a result, have treatment that is unlikely to confer benefit (over-diagnosis/over-treatment). Second, men with clinically significant disease are routinely missed. Inclusion of MRI into the pathway has the potential to reduce both errors. Reduction in the rate of occurrence of these errors is likely to result in overall health gain and possibly reduced NHS costs. The economic considerations of altering the current diagnostic pathway constitute one of our primary objectives.

#### 10.2 Economic analysis

#### 10.2.1 Pilot study

During the pilot phase of the project an initial cost-effectiveness model will be developed. This model will be populated from the pilot study as well as a review of secondary sources of epidemiological, clinical and economic evidence together with appropriately elicited expert opinion. The use of probabilistic sensitivity analysis, value of information methods and scenario analysis  will quantify the uncertainty associated with identifying the most cost effective diagnostic strategy, the costs of that uncertainty (in health and resource terms) and the key uncertainties to resolve with further research. This will inform the inputs into the main economic model. This preliminary cost-effectiveness model will seek to quantify the long-term implication of changes to the diagnostic classification of prostate cancer that result from adoption of alternative diagnostic pathways within the NHS. The implications will relate to the health effects (in terms of quality adjusted life expectancy) and NHS costs of a given diagnostic pathway placing patients into each of the four groups:

- 1. MRI test positive, clinically significant disease
- 2. MRI test negative, clinically significant disease
- 3. MRI test positive, clinically insignificant disease
- 4. MRI test negative, clinically insignificant disease

Clinically significant cancer will be specified by DEFINITIONS ONE and TWO on TPM biopsy. By altering the likelihood of a man falling into any one of these groups, the value of MP-MRI will be assessed by the changes in average outcomes experienced by men and the costs that result. The model will also include the implications of a positive result in the index test concurrent with a negative result in the current standard as well as accounting for the side effect profile of different diagnostic pathways. Structurally, the model will consist of a diagnostic element which will model the probabilities of a given patient falling into each of the diagnostic groups above, and a prognostic element which will estimate the long term implications for health and costs. The specific details of model structure will be informed by a review of existing prostate cancer models including those relating to screening, diagnosis and treatment. In general terms the modelling will adhere to the methods advocated to inform guidance by the National Institute for Health and Clinical Excellence. The preliminary modelling will indicate the main sources of uncertainty associated with the cost-effectiveness of the new pathway. This will inform the final design of main study including the selection of endpoints with respect to this primary objective.

The main phase of the project will provide estimates of key clinical, economic and epidemiological inputs for the model. The most important of these is likely to be the accuracy of the alternative tests (which facilitate estimates of the likelihood of falling into the diagnostic groups detailed above). However, the main phase of the project will also provide a vehicle for the collection of other relevant data to inform cost-effectiveness. These will include the costs of tests and the management of adverse events, and the health-related quality of life (HRQL) implications of any adverse events experienced with tests. The latter will be assessed using the EQ-5D instrument (see Appendix III) as part of the main clinical study. This is a widely used generic measure of HRQL which can be used to derive quality adjusted life years (QALYs). On completion of the data collection for the main phase, the evidence synthesis and modelling undertaken in the first phase will be updated, and the evidence collected in the main study added to it. Ultimately, this work will provide an assessment of the implications of any change that the use of MP-MRI has on under-detection and over-detection. These implications will be in terms of expected quality adjusted survival duration and long-term health service costs. This will allow the value for money of MP-MRI in this context to be assessed using the same metrics employed to evaluate therapeutic technologies by organisations such as NICE.

